7.2. Secondary Efficacy Analyses

7.2.1. Endpoints / Variables

Difference between the Baseline value and the value measured at all the timepoints collected, during the period of study (52 Weeks), at Weeks 4, 8, 16, 24, 32, 42 and 52 visits for below efficacy measures:

- MDS-UPDRS total score
- Total MDS-UPDRS score for Part I
- Total MDS-UPDRS score for Part II
- Total MDS-UPDRS Part III Score
- Total MDS-UPDRS Part IV Score
- Total Neuro-Quality of Life Assessments scores (Neuro-QOL)
- Total Parkinson's disease fatigue scale (PFS-16) Score
- Total Parkinson's disease Questionnaire (PDQ-39) Score
- Visual Analogue Scale (VAS) Score
- Muscle Spasm Scale VAS Score
- Pain Scale VAS score

• Daily dose of Medication to treat Parkinson's Disease

Proportion of subjects requiring reinstatement of PD medication dose following reduction in dose during the study.

7.2.2. Summary Measures

Adjusted Mean using parametric Repeated Measures ANOVA model Median values using Non-parametric method. Contingency tables, with the corresponding heatmaps. Tables containing p-values, in pair-wise manner, with the corresponding heatmaps.

7.2.3. Population of Interest

The secondary efficacy analyses will be based on the Efficacy analysis set population, unless otherwise specified.

7.2.4. Statistical Analyses / Methods

Details of the planned displays are provided in Error! Reference source not found..

7.2.4.1. Statistical Methodology Specification

Secondary endpoints will be analysed using the Mann-Whitney U Test (or Wilcoxon Rank-Sum Test), for the comparison of HB-adMSCs 200MM vs. Placebo.

Sensitivity analysis

Sensitivity analysis will be performed on Efficacy analysis set using a repeated measurements ANOVA model to evaluate the robustness of using parametric method. If the normality of dataset shows significant violation from the presumption of normality, the parametric method will not be performed.

All secondary endpoint efficacy measurements available at post-baseline at scheduled measurements will be analyzed using Repeated Measures ANOVA. The model will include treatment, visits as fixed factors. The within subject factor is visit and with 7 levels (Weeks 4, 8, 16, 24, 32, 42 and 52). The between-subjects factor is treatment (HB-adMSCs 200MM or Placebo).

For Levadopa, the comments will be made about the total number of patients have reduced the dose of medication.

Proportion of subjects requiring reinstatement of PD medication dose

Patients are defined as having reinstated with PD medication if, at any time during the study, their medication dose reinstated up to, or above, their baseline level after it has Page 12 of 15

been reduced. Number of subjects who have reinstated PD dose will be summarized using count and percentage.

Reinstatement is not applicable for patients who did not reduce their dose during the study.

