- 10. Inject the contents into a 250cc bag of normal saline for injection

11. Properly label the infusion bag with the subject ID, D.O.B, preparation date, time and expiration and cover it with an amber bag.

Investigational Product Assignment (Randomization and Blinding)

A total of 24 eligible subjects will be randomized to either placebo (12) or active drug (12) (HB-adMSCs) in a 1:1 balanced design. The randomization will be applicable only to eligible subjects, if a subject is not eligible during the screening process for study participation, this subject shall not me randomized to any group.

Randomization will be conducted using the REDCap randomization module. REDCap does not use an algorithm to dynamically randomize subjects, but rather a pre-determined, stratified and permutated randomization schedule. The module allows for creating a custom allocation list, which serves as a lookup table for deciding how to randomize subjects. The allocation table is stratified to achieve even study treatment distribution within the following subgroups. Raw coded values corresponding to the table are in parenthesis following their representative category.

- Parkinson's severity (Mild vs Moderate):
 - Mild severity (1) (MDS-UPDRS score < 13 AND Carbidopa/levodopa < 375mg/day) (if taking)
 - Moderate severity (2) (MDS-UPDRS > 13 OR Carbidopa/levodopa ≥ 375 mg/day) (if taking)
- Age: ≤ 50 (1) vs > 50 (2)
- Sex: Male (1) vs Female (2)

Controlling Blinded Information

REDCap system's user privileges can be used to allow only certain users to be able to set up the randomization, perform the randomization, or view the allocation information. All REDCap end users will be blinded and will not have access to the randomization information with exception to the unblinded pharmacist and the personnel who will be responsible in setting up the randomization schedule and performing the randomization.

Blinding for Dose Administration

All subjects, investigators, and site staff will be blinded to treatment assigned.

For the preparation of the investigational product, Unblinded pharmacist (UP) will inject the investigational product into a 250 ml sodium chloride (Saline) infusion bag, cover it with an amber plastic bag and apply the label before delivering it to study site.

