	• Change from Baseline in Total Parkinson's disease fatigue scale (PFS-16), at all the timepoints collected during the period of study (52 Weeks)
	Change from Baseline in Total Parkinson's disease Questionnaire (PDQ-39), at all the timepoints

Confidential

Protocol Number: HBPD03 Hope Biosciences Statistical Analysis Plan Date: 18-Apr-2023 Version: 2.0 Status: Final

Objectives	Endpoints
	collected during the period of study (52 Weeks)
	• Change from baseline in Total VAS score
	• Change from baseline in Muscle Spasm Scale VAS score at Week 52
	• Change from baseline in Pain Scale VAS score at Week 52
	 Number of subjects with changes in Daily Dosage of medications taken to treat Parkinson's disease at all the time point during the period of 52 weeks
	 Proportion of subjects requiring reinstatement of PD medication dose following reduction in dose during the study

Confidential

Protocol Number: HBPD03 Hope Biosciences Statistical Analysis Plan Date: 18-Apr-2023 Version: 2.0 Status: Final

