4. ANALYSIS POPULATIONS

Population	Definition / Criteria	Analyses Evaluated
Safety analysis	• All randomised subjects who received at	• Safety
set	least one dose of HB-adMSCs infusion or	 Study Population
	one dose of placebo.	
	• If participants receive a treatment different	
	to their randomized treatment, they will be	
	analysed according to the treatment that	
	was actually received.	
Efficacy	All randomized participants who received	• Efficacy
analysis set	all 6 infusions of either HB-adMSCs or	
	placebo.	
	• Participants will be analysed according to	
	their randomized treatment.	

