10.1.2. Handling of Missing Data

Element	Reporting Detail	
General	Missing data occurs when any requested data is not provided, leading to blank fields on the collection instrument:	
	 If only some of the values within the test are missing, those fields will be marked as "blank". Otherwise, if all data for a specific visit are missing, the data will be completely excluded from the table. Answers such as "Not applicable" and "Not evaluable" are not considered to be missing data and should be displayed as such. 	
Outliers	• Any participants with outlying results may be excluded in additional ad hoc summaries and/or statistical analyses. These will be documented along with the reason for exclusion in the clinical study report, but the primary conclusions will remain based on the full population sets.	

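### The medication-reinstatement percentage appears to be taken among patients who first reduced their dose, a group formed after randomisation, so it cannot be read as a treatment comparison

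*SAP*

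**What the plan says.** The SAP's objectives and endpoints table and section 7.2.1 both list this secondary efficacy endpoint: "Proportion of subjects requiring reinstatement of PD medication dose following reduction in dose during the study".

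Section 7.2.4.1 defines the event. A patient counts if, at any time in the study, "their medication dose reinstated up to, or above, their baseline level after it has" been reduced. The planned output is: "Number of subjects who have reinstated PD dose will be summarized using count and percentage". The next sentence is: "Reinstatement is not applicable for patients who did not reduce their dose during the study". No denominator is written out.

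The same section opens with a general rule: "Secondary endpoints will be analysed using the Mann-Whitney U Test (or Wilcoxon Rank-Sum Test), for the comparison of HB-adMSCs 200MM vs. Placebo". It makes no exception for this endpoint and names no test for a yes/no outcome. Section 7.2.3 places secondary efficacy analyses on the Efficacy analysis set, which section 4 limits to patients who received "all 6 infusions of either HB-adMSCs or" placebo.

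**The concern.** A patient can reinstate only after reducing. If patients who did not reduce drop out of the percentage, each arm is represented by a subgroup that formed after randomisation. Should the product allow some additional patients to reduce, and should those patients be less stable on the lower dose, they enter the active arm's denominator and some enter its numerator. They have no counterparts among the placebo reducers. The active percentage can then rise even though more active patients stay below their baseline dose.

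A higher reinstatement percentage on HB-adMSCs could therefore mean less durable reductions, a wider group of patients attempting reduction, or chance. The planned output does not separate these. With 12 patients per arm the denominators may also be very small.

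**Working it through.** **Inputs from the documents.** 24 patients, 12 per arm (protocol, Investigational Product Assignment). Reinstatement means return to or above the baseline dose after a reduction (SAP 7.2.4.1). The documents give no reduction or reinstatement rates, so there is no planned figure to reproduce, and every rate below is an assumption.

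**Set-up.** Group A reduces under either arm: 25% of patients, or 3 of 12, of whom one third reinstate in both arms. Group B reduces only if given HB-adMSCs: 33% of patients, or 4 of 12. Its reinstatement rate *r* is varied.

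- Active arm: reducers = 3 + 4 = 7; reinstated = 3 × 1/3 + 4*r* = 1 + 4*r*; sustained = 7 − (1 + 4*r*) = 6 − 4*r*.
- Placebo arm: reducers = 3; reinstated = 1; sustained = 2.

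**Expected results, active vs placebo.**

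| Group B | Reinstated, of reducers | Reinstated, of all 12 | Sustained, of all 12 |
|---|---|---|---|
| *r* = 50% | 3/7 = 43% vs 1/3 = 33% | 3/12 = 25% vs 1/12 = 8% | 4/12 = 33% vs 2/12 = 17% |
| *r* = 33% | 2.33/7 = 33% vs 33% | 2.33/12 = 19% vs 8% | 4.67/12 = 39% vs 17% |
| *r* = 10% | 1.4/7 = 20% vs 33% | 1.4/12 = 12% vs 8% | 5.6/12 = 47% vs 17% |
| No group B | 1/3 vs 1/3 | 1/12 vs 1/12 | 2/12 vs 2/12 |

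The first row shows the reversal: active looks worse among reducers and better on sustained reduction. In the second row the reducer percentages tie and hide the difference. In the third the reducer percentage favours active. In the last, treatment does not affect who reduces and there is no bias.

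The third column shows that a full denominator alone does not help. Reinstatement over all 12 is higher on active in every row with a group B, because more reductions create more chances to reinstate.

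**Sampling variation in the first row.** Over 400,000 simulated trials, both reducer percentages were defined in 96.8%. Among those, the percentage was higher on active in 59% and lower in 35%. Over all simulated trials, sustained reduction favoured active in 76.5%. These differences are far from detectable: Fisher's exact p is 1.0 for 3/7 vs 1/3 and 0.64 for 4/12 vs 2/12.

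**Size of the denominators.** If a fraction *p* of a 12-patient arm reduces, the chance of no reducers is (1 − *p*)^12, and the chance of two or fewer is the binomial lower tail.

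| *p* | No reducers | Two or fewer |
|---|---|---|
| 10% | 28% | 89% |
| 25% | 3.2% | 39% |
| 50% | 0.02% | 2% |

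With 1 of 2 reinstated, the exact 95% interval runs from 1 − √0.975 = 1.3% to √0.975 = 98.7%.

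**The case against.** The strongest reply is that the SAP does not say what it is being criticised for. The denominator is inferred. Section 10.1.2 says that not-applicable answers "are not considered to be missing data and should be displayed as such", so a table over all patients with a not-applicable row is also a fair reading. The endpoint's own text is descriptive, and only the general Mann-Whitney sentence suggests a test. Section 2.3 makes secondary endpoints exploratory, and the Holm list in section 5.4 omits this one. Other outputs are not conditioned on reduction: daily dose at each visit, the number of patients with dosage changes, and a comment on how many reduced levodopa. Among reducers, durability is also a legitimate descriptive question.

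Most of this stands and limits the point. It does not remove it. Under the all-patient reading, reinstatement still counts against the arm with more reductions, as the third column shows. The count of dosage changes gives no direction, the levodopa comment covers one drug, and no planned output reports who reduced and stayed below baseline. A side-by-side percentage for a listed efficacy endpoint will be read as a comparison.

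A reader might also infer that reducers are created by treatment response. The documents give no rule or reason for dose reductions, so they support only that treatment may influence who reduces.

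**Conclusion.** The concern holds in a limited form. The SAP implies a reducers-only percentage, and that percentage is not protected by randomisation. Its direction can differ from that of sustained reduction: 43% vs 33% reinstated among reducers alongside 33% vs 17% sustained, under assumed rates. This needs treatment to affect who reduces, and the extra reducers to reinstate more often than the rest. If they reinstate equally often, the percentage hides the difference. If they reinstate less often, it favours active.

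The documents do not support the stronger inference that the planned result will point the wrong way, or that the SAP commits to a formal test on this subset alone. The primary conclusion is unaffected. The change is still worth making, because the endpoint is listed as efficacy, its denominator is unstated, and a clearer measure can be built from data already collected.

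**What to change.** In SAP section 7.2.4.1, report the following by arm over all randomised patients taking Parkinson's medication at baseline. Show those on none separately, since they cannot reduce; the protocol's severity strata already allow for patients not taking carbidopa/levodopa. Use all randomised patients because the Efficacy set's requirement of six infusions is itself a selection made after randomisation. The categories are exclusive:

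1. Never reduced.
2. Reduced and never reinstated, below baseline at Week 52.
3. Reduced and reinstated at any time, including those who later reduced again.
4. Week 52 dose missing, for patients not already in category 3.

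Use category 2 as the between-arm measure: a difference in proportions with an exact confidence interval, and Fisher's exact test if a test is wanted, labelled exploratory. This replaces the Mann-Whitney test for this endpoint. State in advance how category 4 counts in the denominator. Keep any reducers-only percentage as descriptive, with numerator and denominator printed, and say that it is not a treatment comparison.

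The cost is SAP wording and one extra table. Concomitant medications are already recorded at every visit (protocol Table 3), so the schedule needs no new data collection. Intervals will be wide at about 12 per arm.

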8. SAFETY ANALYSES

The safety analyses will be based on the Safety analysis set, unless otherwise specified.

8.1. Adverse Events Analyses

AEs will be coded using the most recent version of the Medical Dictionary for Regulatory Activities (MedDRA).

A treatment emergent adverse event (TEAE) is defined as an event that has onset date on the first day of exposure or after the first day of exposure to infusion treatment, and no later than 3 days after the last day of infusion treatment. AEs with missing start and/or stop dates will be assumed to be treatment emergent.

Treatment adverse events (TAE) are summarised descriptively, whereas non-TEAEs are presented in listings. TAE data will be displayed in terms of the number of subjects with at least one event (N), percentage of subjects with at least one event (%) and the number of events E.

Summaries of TAE and of serious AEs will be presented as an overview, including all AEs, AEs listed by severity, serious AEs, AEs by relation to treatment, action taken after AEs occurred and treatment advised, and the outcome of AEs.

Furthermore, summary tables based on system organ class and preferred terms are made for:

- All TAEs
- Serious AEs
- AEs leading to withdrawal of study

Individual adverse events will be listed.

The details of the planned displays are in Error! Reference source not found..

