	Placebo: Saline Solution 0.9%						
	Dose: N/A						
	Route: Intravenous						
	Regimen: Weeks 0, 4, 8, 16, 24 and 32.						
Duration of administration	1 hour						
Laboratory Samples.	Screening, Week 0, 24 and 52.						
Visits by Weeks	Screening						
	Week 0 – Infusion 1						
	Week 4 – Infusion 2						
	Week 8 – Infusion 3						
	Week 16 – Infusion 4						
	Week 24 – Infusion 5						
	Week 32 – Infusion 6						
	Week 42 – Follow Up.						
	Week 52 – End of Study						

"A Randomized, Double-Blind, Single Center, Phase 2, Efficacy and Safety Study of autologous HB-adMSCs vs Placebo for the Treatment of Patients with Parkinson's Disease"

Introduction

Objectives

Primary Objective:

• To investigate the safety and efficacy of intravenous infusions of HB-adMSCs vs Placebo in patients with Parkinson's disease as determined by improvements in Quality of Life as measured by the MDS UPDRS assessment. (Time frame: Baseline to Weeks 4, 8, 16, 24, 32, 42 and 52).

Secondary Objective:

• To evaluate the safety and efficacy of intravenous infusions of HB-adMSCs vs Placebo in patients with Parkinson's disease as, determined by changes in disease assessments and dosage of medications. (Time frame: Baseline to Weeks 4, 8, 16, 24, 32, 42 and 52).

Endpoints

Primary Endpoints

The safety and efficacy endpoints of this study will be evaluated by assessing changes from Baseline to Weeks 52 in the following:

- Changes in MDS-UPDRS Part II from Baseline to Week 52. Motor Aspects of Experiences of Daily Living (M-EDL), including speech, saliva and drooling, chewing and swallowing, eating tasks, dressing, hygiene, handwriting, doing hobbies and other activities, turning in bed, tremor, getting out of bed, a car, or a deep chair, walking and balance and freezing.
- Incidence of treatment-emergent Adverse Event (TEAEs) and serious Adverse Events (SAEs).
- Incidence and risk of AEs of special interest (serious or nonserious), including thromboembolic events, peripheral events defined as, thromboembolism of the extremities, also infections and hypersensitivities.
- Clinically significant changes in laboratory values, vital signs, weight and physical examination results.

Secondary Endpoints

The safety and efficacy endpoints of this study will be evaluated by identifying changes from Baseline to Weeks 4, 8, 16, 24, 32, 42 and 52 in the following:

- Changes in MDS-UPDS Part I, III, IV, or total score.

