• To investigate the safety and efficacy of intravenous infusions of HB-adMSCs vs Placebo in patients with Parkinson's disease as determined by improvements in Quality of Life, estimated by the MDS UPDRS assessment. (Time frame: Baseline to Weeks 4, 8, 16, 24, 32, 42 and 52). A battery of statistical tests will be applied, where suitable and applicable. Tests will include the report of parametric or non-parametric statistical tests, with the corresponding p-values, presented in pair-wise manner, as well as contingency tables, representing answers in their native form.	 Change from Baseline in Total MDS-UPDRS Part II, only at Week 52 Number of treatment-emergent Adverse Event (TEAEs) during 52 week period Number of serious Adverse Events (SAEs) during the period of 52 weeks Number of AEs of special interest includes thromboembolic events, peripheral events defined as thromboembolism of the extremities, infections and hypersensitivities Change from baseline in clinical parameters, measured at the end of the study (52 weeks): Physical examination Electrocardiogram (ECG) Pulse Systolic blood pressure Body weight BMI Change from baseline in laboratory assessments at the end of the study (52 weeks):

Protocol Number: HBPD03

Date: 18-Apr-2023 Version: 2.0 Hope Biosciences Statistical Analysis Plan Status: Final

Objectives	Endpoints
	o Biochemistry
	 Haematology
	 Urinalysis
Secondary Objectives	Secondary Endpoints
To evaluate the safety and efficacy of intravenous infusions of HB-adMSCs vs Placebo in patients with Parkinson's disease based on	Change from Baseline in MDS- UPDRS Total score, at all the timepoints collected, during the period of study (52 Weeks)
changes in disease assessments and dosage of medications. (Time frame: Baseline to Weeks 4, 8, 16, 24, 32, 42 and 52).	 Change from Baseline in Total MDS- UPDRS Part I, at all the timepoints collected during the period of study (52 Weeks)
	 Change from Baseline in Total MDS- UPDRS Part II, at all the timepoints collected during the period of study (52 Weeks)
	 Change from Baseline in Total MDS- UPDRS Part III at all the timepoints collected during the period of study (52 Weeks)
	 Change from Baseline in Total MDS- UPDRS Part IV, at all the timepoints collected during the period of study (52 Weeks)
	 Change from Baseline in Total Neuro- Quality of Life Assessments scores (Neuro-QOL), at all the timepoints collected during the period of study (52 Weeks)

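### The TEAE definition in SAP 8.1 stops 3 days after the last infusion, but the primary safety endpoint counts TEAEs over 52 weeks

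*SAP*

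**What the plan says.** The SAP's objectives and endpoints table lists, under the primary objective, "Number of treatment-emergent Adverse Event (TEAEs) during 52 week period". It lists serious events over the same 52 weeks as a separate item, and events of special interest as another.

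The protocol's Primary Endpoints section opens with "The safety and efficacy endpoints of this study will be evaluated by assessing changes from Baseline to Weeks 52 in the following" and includes TEAE incidence in the list that follows. Its Secondary Endpoints section lists TEAE incidence again, at visits that include Weeks 42 and 52. The protocol gives no TEAE window of its own.

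SAP 8.1 sets the window: onset on or after the first day of exposure and "no later than 3 days after the last day of infusion treatment". An event with a missing start or stop date is assumed to be treatment-emergent. Treatment adverse events are summarised by number of subjects, percentage and number of events, "whereas non-TEAEs are presented in listings". The tables by system organ class and preferred term cover all TAEs, serious AEs and "AEs leading to withdrawal of study".

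The protocol's Investigational Plan and its Adverse Event Reporting Period section both run safety follow-up to about 20 weeks after the last dose. Adverse events are assessed at Visit 8 (Week 42) and Visit 9 (Week 52).

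**The concern.** The endpoint names a 52-week period, but the definition of the event being counted ends soon after Week 32. Neither document reconciles the two. Read literally, SAP 8.1 yields a TEAE count that does not cover the period its own primary safety endpoint states, and almost none of the 20-week safety follow-up can contribute to it.

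The events at risk are those that are fully dated, non-serious, start in follow-up and do not lead to withdrawal. On the visible text they appear only in listings, with no clearly assigned by-arm summary. A late non-serious infection is one example: infections are of special interest, but SAP 8.1 names no table for events of special interest. Another is a laboratory abnormality recorded as an adverse event with onset at the Week 52 draw, since the scheduled post-baseline draws are only at Weeks 24 and 52. The laboratory values themselves are analysed separately under SAP 8.2.

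The missing-date rule makes the count less consistent. A late event with no recorded stop date is counted, while a late event with both dates is not.

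**Working it through.** **Inputs**

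- Last scheduled infusion: Week 32 (SAP 2.2; protocol Study Summary).
- End of study: Week 52 (same places).
- TEAE window closes 3 days after the last infusion (SAP 8.1).
- Safety follow-up: 20 weeks (protocol Investigational Plan).
- Visit windows: ±7 days at Infusion 6 and at end of study (protocol Table 3).

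Days are counted from the first infusion as day 0. The last day of infusion treatment is taken to mean the participant's own last infusion.

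**The plan's own figure.** 52 − 32 = 20 weeks = 140 days, which matches the stated follow-up.

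**All six infusions, nominal schedule**

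- Last infusion: 32 × 7 = day 224.
- Window closes: 224 + 3 = day 227.
- End of study: 52 × 7 = day 364.
- Outside the window: 364 − 227 = 137 days.
- Share of the study: 137/364 = 37.6%.
- Share of the safety follow-up: 137/140 = 97.9%.

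With the SAP 10.1.1 convention (first dose = Study Day 1), the window closes on Day 228 and the study ends on Day 365, so the share is 137/365 = 37.5%.

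**Visit windows.** Infusion 6 can fall on day 217 to 231, so the window closes on day 220 to 234. End of study can fall on day 357 to 371.

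- Smallest share: (357 − 234)/357 = 123/357 = 34.5%.
- Largest share: (371 − 220)/371 = 151/371 = 40.7%.

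**Infusions stopped early, assuming follow-up still runs to day 364**

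| Last infusion | Window closes | Days outside | Share outside |
|---|---|---|---|
| Week 24 | 171 | 193 | 53.0% |
| Week 16 | 115 | 249 | 68.4% |
| Week 8 | 59 | 305 | 83.8% |
| Week 4 | 31 | 333 | 91.5% |
| Week 0 | 3 | 361 | 99.2% |

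Participants who leave the trial may be followed for less time. For those who received a single dose, the protocol plans a visit about 30 days later. The share outside is then (30 − 3)/30 = 90.0% of that follow-up. The documents do not say how many participants will stop early.

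**The case against.** The strongest reply is that the texts can be read together: 52 weeks is the observation period, and the endpoint counts whichever events in it meet the SAP 8.1 definition. On that reading the protocol's reporting period shows only that late events are collected, not that they are TEAEs. The 3-day limit also matches the 72-hour windows in the protocol's Study Stopping Rules, so it may be a deliberate on-treatment definition.

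This does not dispose of the point. The reading leaves the 52-week wording with no effect, and it sits badly with the protocol listing TEAE incidence at Weeks 42 and 52. The documents do not give the 72-hour parallel as the reason for the window. If an on-treatment count was intended, the endpoint should say so.

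Other parts of the reply stand and limit the reach:

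- Serious events and withdrawals have their own tables with no stated TEAE limit. Special-interest events are a separate endpoint not worded as treatment-emergent.
- SAP 8.1 uses TAE without defining it. I take it to mean TEAE because the same sentence contrasts it with non-TEAEs.
- The overview is unclear in scope: "Summaries of TAE and of serious AEs will be presented as an overview, including all AEs". It may or may not bring in late non-serious events.
- The display list cannot be seen: "The details of the planned displays are in Error! Reference source not found". A whole-period table there would remove most of the practical harm, but not the conflict in wording.
- With 24 participants, late events can be read from the listings, though not as a by-arm summary.

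**Conclusion.** The concern holds. As written, the TEAE definition and the primary safety endpoint cover different periods. For a participant with all six infusions, 137 of 364 days (37.6%; 34.5% to 40.7% with visit windows) lie outside the definition, including 137 of the 140 follow-up days. The larger shares for early stopping depend on follow-up to Week 52 and apply to an unknown number of participants. All these figures are shares of time; nothing in the documents converts them to numbers of events.

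The consequence is limited to a descriptive summary. No data are lost, and the tested primary hypothesis (MDS-UPDRS Part II, SAP 2.3) is unaffected. It should be fixed because a named primary safety endpoint cannot be produced over its stated period under the definition given.

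**What to change.** Choose one of two routes in SAP 8.1:

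1. Define a TEAE as an adverse event with onset or worsening from the start of the first infusion to the end of the participant's study follow-up (the Week 52 visit for completers). No follow-up time then lies outside the definition. Report follow-up time by arm beside the counts. This shows any imbalance in follow-up but does not correct for it.
2. Keep the 3-day window under its own name as an on-treatment table, and add a by-arm summary of all adverse events over the whole period as the primary safety endpoint.

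Under either route, use one defined abbreviation in place of TAE and TEAE, and restore the reference to the display list. As a side point, limit the missing-date rule to missing start dates, so that a missing stop date does not decide the status of an event whose onset is known.

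The cost is SAP wording and one programming flag (plus a table under route 2), using data already collected. A wider window brings more background events into both arms; a separate on-treatment table would show these apart. The SAP is marked final, and SAP 5.5 gives some sponsor members unblinded interim results, so the amendment should be dated and its timing relative to that access recorded.
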